Patients with progressive disease after two cycles (defined as a clear increase in bone marrow blast count, typically a > 50% increase in bone marrow blasts over baseline) should be removed from study.

Patients with stable disease may continue on study and should undergo a diagnostic bone marrow biopsy at the end of even numbered cycles.

Once AML patients achieve morphologic complete remission with incomplete blood count recovery (CRi) or MDS patients achieve a marrow complete response (Marrow CR) as defined in Section 9.0, decitabine administration may be decreased to 20 mg/m²/day for ten consecutive days every 6 weeks, to limit myelosuppressive toxicity and improve count recovery. After 2 cycles at 6 week intervals, the dose may be reduce to 20 mg/m²/day for five consecutive days in 6 week cycles, at the discretion of the treating physician. After two cycles of five consecutive days of treatment, if the patient meets the definition of CR with complete cytogenetic response as defined in Section 9.0, administration may further be decreased to three consecutive days per cycle at the discretion of the treating physician.

Sample collection for correlative studies:

Bone marrow biopsies should be performed at baseline, at Cycle 1 Day 10 ± 1, and at Day 28 ± 4 of Cycles 1, 2, 4, and 6. Following Cycle 6, bone marrow biopsies should be performed at the discretion of the treating physician to assess for relapse or progression.

Peripheral blood samples should be collected on Day 4± 1 of Cycle 1. Collection should be obtained 45 ± 15 minutes after decitabine infusion is initiated.

Genomic Predictors of Decitabine Response in AML/MDS

Table of Contents

Section	Page
Section 4.21.0 INTRODUCTION	7
1.1 Rationale.....	7
1.2 Decitabine and Hypomethylating agents in AML/MDS.....	9
1.2.1 Pharmacokinetics and Metabolism of Decitabine.....	11
1.2.2 Experience with extended dosing schedules.....	12
1.3 Correlative Studies	13
2.0 OBJECTIVES.....	15
2.1 Primary Objective.....	15
2.2 Secondary Objectives	15
3.0 PATIENT SELECTION.....	16
3.1 Inclusion Criteria	16
3.2 Exclusion Criteria.....	16
3.3 Inclusion of Women and Minorities.....	17
4.0 REGISTRATION PROCEDURES	18
4.1 Confirmation of Patient Eligibility.....	18
4.2 Patient Registration in the Siteman Cancer Center Database.....	18
4.3 Assignment of UPN.....	18
5.0 INVESTIGATIONAL PLAN	20
5.1 Summary of Study Design.....	20
5.2 Study Procedures	20
5.2.1 Pre-study Procedures.....	20
5.2.2 Baseline Evaluation.....	21

1.0 INTRODUCTION

1.1 Rationale

Personalized therapy for cancer requires that 1) patient-specific factors (e.g. patient-specific mutations, expression profiles, or pharmacogenomics) influence treatment algorithms, and 2) once therapy is initiated, *in vivo* responsiveness is used to guide further therapy. The modern era of genomics has provided significant insights into cancer pathogenesis by describing patterns of germline and somatic variants, as well as defining disease-specific patterns of gene expression. However, the application and integration of this data with therapeutics remains a difficult task.

Decitabine is a commonly used single-agent therapy for patients with acute myeloid leukemia (AML) and/or myelodysplastic syndrome (MDS). Historically, it has yielded clinical complete responses in approximately 25% of patients across diverse clinical trials, it is well tolerated, and it can be given as in the outpatient setting. However, the majority of patients do not respond to decitabine, the molecular etiology of decitabine sensitivity is unknown, and there are no algorithms to predict patient responsiveness *a priori* or even within one month of starting therapy.

AML and MDS are two closely related hematological disorders characterized by ineffective hematopoiesis and malignant expansion of clonal myeloid cells. Both AML and MDS frequently occur in elderly patients and some cases are secondary and/or related to long-term bone marrow damage after radiation or chemotherapy. Current therapy for AML consists of cytotoxic chemotherapy followed by consolidation chemotherapy or stem cell transplantation. Using these approaches, current cure rates may be as high as 60% for patients younger than 60 with good risk cytogenetics (e.g. t(15;17), t(8;21), inv(16)).[4] Outcomes in patients ≥ 60 years old and with relapsed disease remain poor with 2 year survival of only ~25%.[5] Historically, the available treatment for MDS has been symptomatic and has not been shown to be effective in producing sustained improvement in hematopoiesis or in delaying leukemic evolution[6, 7].

Current AML therapy is poorly tolerated in elderly and pre-treated patients due to hematologic and non-hematologic toxicities; following such therapy, patients typically require 3-4 weeks of hospitalization for treatment of neutropenic fevers and for regular transfusions. Even among the relatively healthy patients enrolled in clinical trials, induction mortality in the elderly can be as high as 20-40% following standard induction therapy,[8-11] and moderate to severe non-hematologic toxicity occurs in at least an additional 30% of patients.[9, 12-14] Consequently, many older AML patients are not offered traditional intensive chemotherapy, but receive supportive care alone.[15] More effective and less toxic therapies are needed to provide durable remissions in a significant proportion of elderly AML in populations.

[REDACTED]

[REDACTED]

[REDACTED]

[REDACTED]

We and others have recently used whole genome sequencing to identify recurrent, somatic mutations in AML and MDS patients in four genes that are involved in methylcytosine regulation: *DNMT3A*, *IDH1*, *IDH2*, and *TET2*. [29-37] Collectively, nearly half of all AML/MDS patients have a mutation in one of these four genes. *DNMT3A* mutations are associated with an adverse outcome in AML patients treated with cytotoxic chemotherapy. [35, 38] However, it is not yet clear whether the presence of mutations in one or more of these genes is associated with response or resistance to decitabine.

In this study, we will treat patients with the current state-of-the-art decitabine schedule.[3] We will perform exome sequencing on all patients and correlate response with mutation status, rate of mutation clearance, expression profile, plasma decitabine levels, and DNA methylcytosine content reduction. This approach will comprehensively assess genomic and pharmacologic parameters that could clinically predict patient response to decitabine.

In this study, we will combine analysis of patients with AML and MDS. Recent genomic analysis has shown that AML and MDS have shared mutations in many of the same genes, shared patterns of mutation acquisition, and shared patterns of mutation evolution.[39, 40] Furthermore, MDS, like AML, presents with clonal hematopoiesis, even when the morphologic blast count is zero.[36] Because this study will identify and track the rate of clearance of patient specific mutations, and because decitabine has been shown to have efficacy in both AML and MDS patients, [2, 3, 16-19, 41-45] combining analysis of AML and MDS patients is reasonable. Asymptomatic MDS patients are excluded because these patients are typically followed with watchful-waiting rather than with chemotherapy.

[REDACTED]

[REDACTED]

[REDACTED]

[Redacted text block]

[Redacted text block]

[Redacted]	[Redacted]	[Redacted]	[Redacted]	[Redacted]
[Redacted]	[Redacted]	[Redacted]	[Redacted]	[Redacted]
[Redacted]	[Redacted]	[Redacted]	[Redacted]	[Redacted]
	[Redacted]	[Redacted]	[Redacted]	[Redacted]
	[Redacted]	[Redacted]	[Redacted]	[Redacted]
	[Redacted]	[Redacted]	[Redacted]	[Redacted]
	[Redacted]	[Redacted]	[Redacted]	[Redacted]
[Redacted]	[Redacted]	[Redacted]	[Redacted]	[Redacted]
	[Redacted]	[Redacted]	[Redacted]	[Redacted]
	[Redacted]	[Redacted]	[Redacted]	[Redacted]
[Redacted]	[Redacted]	[Redacted]	[Redacted]	[Redacted]
[Redacted]	[Redacted]	[Redacted]	[Redacted]	[Redacted]
[Redacted]	[Redacted]	[Redacted]	[Redacted]	[Redacted]

[Redacted text block]

[Redacted text block]

[Redacted text block]

[Redacted text block]

[Redacted text block]

[Redacted text block]

[Redacted text block]

[Redacted text block]

[Redacted text block]

[REDACTED]

[REDACTED]

[REDACTED]

[figure not shown]
[REDACTED]	[REDACTED]	[REDACTED]
[REDACTED]	[REDACTED]	[REDACTED]
[REDACTED]	[REDACTED]	[REDACTED]
[REDACTED]	[REDACTED]	[REDACTED]
[REDACTED]	[REDACTED]	[REDACTED]
[REDACTED]	[REDACTED]	[REDACTED]
[REDACTED]	[REDACTED]	[REDACTED]
[REDACTED]	[REDACTED]	[REDACTED]
[REDACTED]	[REDACTED]	[REDACTED]
[REDACTED]	[REDACTED]	[REDACTED]

[REDACTED]

[REDACTED]

[REDACTED]

[REDACTED]

1.3 Correlative Studies

With exception of the peripheral blood sample collected on Cycle 1 Day 4, all correlative studies will be collected under HRPO# 201011766 (“Tissue Acquisition for Analysis of Genetic Progression Factors in Hematologic Diseases”) that all patients will be concurrently enrolled in. The goals of the correlative studies include:

1. To correlate patient-specific mutations with response to decitabine.
We will perform exome sequencing of each patient’s pre-study bone marrow sample and skin sample. We will determine AML/MDS-associated variants found in the bone marrow, but not skin sample. We will correlate the presence of mutations with response (especially mutations in *DNMT3A*, *IDH1*, *IDH2*, and *TET2*). This study is powered to identify mutations with >80% sensitivity to predict decitabine response if used as a clinical assay.
2. To correlate the velocity and depth of response with response to decitabine.
We will assess tumor burden by allele frequency of patient-specific mutations in bone marrow samples collected pre study, Cycle 1 Day 10±1, Cycle 1 Day 28±4, and Cycle 2 Day 28±4. We will assess mutations in at least 24 recurrently mutated genes (including, but not limited to: *FLT3*, *DNMT3A*, *NPM1*, *TET2*, *WT1*, *IDH1*, *IDH2*, *RUNX1*, *NRAS*, *TP53*, *U2AF1*, *KRAS*, *PHF6*, *MSTP9*, *PTPN11*, *KIT*, *SMC3*, *PRUNE2*, *ETV6*, *CEBPA*, *SMC1A*, *ASXL1*, *STAG2*, *RAD21*) as well as all patient-

specific mutations discovered during exome sequencing. The leukemic allele frequency will be measured using the Illumina MySeq or HiSeq platform using DNA capture by gene specific biotinylated-oligonucleotides. Patient bone marrow samples will be assessed pre-study, Cycle 1 Day 10 \pm 1, Cycle 1 Day 28 \pm 4, and Cycle 2 Day 28 \pm 4 and compared with patient specific skin samples (normal control). The velocity of response will be calculated as the natural log rate of patient-specific mutation allele frequency clearance. Depth of response will be defined as the lowest patient-specific mutation allele frequency in a bone marrow sample. The velocity and depth of tumor response will be correlated to:

- Achievement of clinical CR,
- Time to best response,
- Mutational status,
- Time to disease progression.

Because all patient-specific exome-discovered mutations will be assessed a second time in the primary bone marrow sample as well as the Cycle 1 Day 10 \pm 1, Cycle 1 Day 28 \pm 4, and Cycle 2 Day 28 \pm 4 bone marrow samples, this study will also serve to validate all exome-discovered mutations. This is important, because exome sequencing is associated with a 20-50% false-discovery rate depending on type I error tolerated (mutation-calling algorithms are typically set for greater sensitivity than specificity). Thus, many mutations discovered during exome sequencing are incorrect. This second analysis of these mutations will server to exclude these false positive calls.

3. To correlate the bone marrow expression profile from pre-study and Cycle 1 Day 10 \pm 1 with response to decitabine.

We will correlate expression signatures, and changes in expression signatures, with:

- Achievement of clinical CR,
- Mutation status.

4. To correlate steady-state plasma decitabine concentration on Cycle 1 Day 4 \pm 1 with:
 - Achievement of CR.

5. To correlate the extent of bone marrow DNA hypomethylation on Cycle 1 Day 10 \pm 1 with response to decitabine.

We will assess the percent reduction in bone marrow methylcytosine content using LC-MS. Patients will be evaluated pre-study and Cycle 1 Day 10 \pm 1. The change in DNA methylcytosine content will be correlated to:

- Achievement of clinical CR,
- Change in expression signature.

This will determine whether inadequate blast exposure to decitabine correlates with drug resistance.

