5.2.9 Cycles 1, 2, 4 and 6 Day 28 ± 4 days

Bone marrow aspirate and biopsy. Standard bone marrow procurement procedures will be followed for collection of the tissue. Assessments performed on bone marrow will include: correlative studies (collected under HRPO# 201011766), morphologic assessment, cytogenetics, and FISH.

Patients who achieve with clinical response (CRi or better) and are receiving cycles every 6 weeks, will undergo bone marrow biopsies on day 42 ± 4.

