14.2.3 Secondary Endpoint Analyses

The overall response rate (CR/CRi/PR) and complete response rate (CR/CRi) will be compared with historical controls[2], and the 95% confidence intervals will be provided.

The rate of patient specific mutation clearance after 10, 28, and 56 days of therapy will be determined using an Illumina based platform. We will compare the rate of mutation clearance between the patients who achieve a CR/CRi after 4 cycles and those who do not. We anticipate that we will identify between 6 and 25 exonic SNVs per case (the range obtained with >200 AML samples sequenced to date with whole genome or exome sequencing), and that the expected 95% confidence

interval of the mean variant allele frequency will be $\pm 2.56\%$ and $\pm 1.25\%$, respectively, if we assume an anticipated standard deviation of 3.2% within the same clone. The change of tumor burden over time and its association with clinical response will be assessed using 2-way ANOVA for repeated measurement data, followed by the ad-hoc multiple comparisons for between-group differences (e.g., responders vs. non-responders) at given time points as well as the between-time differences within each group. The resultant critical P values will also be corrected using permutation analysis for multiple testing.

The steady-state plasma decitabine concentration on day 4 ± 1 will be measured and correlated with clinical overall response.

The percent decrease in bone marrow methylcytosine will be calculated on day 10 ± 1 . We will compare this reduction with previously published data and between the patients who achieve CR/CRi and those who do not. The correlation of peak plasma levels of decitabine with response will be assessed using 2-sample t-test or Mann-Whitney non-parametric rank-sum test as appropriate. The change of total bone marrow DNA methylcytosine from baseline and its association with both steady-state plasma drug levels and response will be assessed using 2-way ANOVA for repeated measurement data, followed by the ad-hoc multiple comparisons for between-group differences (e.g., responders vs. non-responders) and between-time differences. Similar analyses will be performed for the correlation of expression profiles and SNP analysis with pharmacokinetic data.

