Statistical power justification. A power analysis was performed using two-sample t-test for between-group difference and paired t-test for the change over time. For tumor clearance, this will provide $> 99\%$ power to detect a 10% difference in the means at two separate time points for clones with 6 or more variants, and $> 98\%$ power to detect a 15% difference if there are 3 or more variants per clone with $\alpha = 0.05$ (power will decrease to 91% and 82%, respectively, in cases where the standard deviation is 4.7%, the maximum we have observed thus far). For pharmacologic correlations, we anticipate 85% power to determine a 25 ng/ml difference between the average C_{\max} of 45 evaluable responders and 55 evaluable non-responders with an anticipated average C_{\max} of 70 ng/ml and a standard deviation of 40 ng/ml within the entire cohort, and with $\alpha = 0.05$. [22] We believe a less significant difference would not be sufficient to warrant application in clinical decision making (i.e. whether to continue therapy for more than 1 cycle). We anticipate 99% power to determine a difference of 20% in the reduction of bone marrow methylcytosine between 45 evaluable responders and 55 evaluable non-responders with an expected standard deviation of 15% and $\alpha = 0.05$. [28, 66-68] The difference in methylcytosine reduction previously observed was 30% between patients achieving CR/PR and those with only hematologic improvement. [28]

Time to relapse and time to death will also be listed for each patient.

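### Depth of mutation clearance is a minimum with no fixed sample and no landmark, so it depends on variant count and on how long a patient stays progression-free; the change-over-time power figures do not come from the paired test named

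*Combined protocol and SAP*

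**What the plan says.** Section 1.3 (Correlative Studies) gives two clearance biomarkers. For depth: "Depth of response will be defined as the lowest patient-specific mutation allele frequency in a bone marrow sample". For velocity: "The velocity of response will be calculated as the natural log rate of patient-specific mutation allele frequency clearance". Both use "bone marrow samples collected pre study, Cycle 1 Day 10±1, Cycle 1 Day 28±4, and Cycle 2 Day 28±4", and both are to be correlated with achievement of CR, time to best response, mutational status and time to disease progression. Section 1.3 does not say which variants enter the minimum, whether it runs within one marrow or across marrows, or what to do when a marrow is missing.

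Section 14.2.3 plans on these counts: "We anticipate that we will identify between 6 and 25 exonic SNVs per case". It names the time points: "The rate of patient specific mutation clearance after 10, 28, and 56 days of therapy". The change in tumor burden and its association with response are to be "assessed using 2-way ANOVA for repeated measurement data". That section works with the mean allele frequency and gives no analysis of depth. Its power paragraph names a two-sample t-test for group differences and a paired t-test for change over time, then quotes power for a 10% "difference in the means at two separate time points for clones with 6 or more variants" and for a 15% difference with three or more.

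Section 5.2.9 and footnote d of Appendix 2 add that patients with CRi or better who are "receiving cycles every 6 weeks, will undergo bone marrow biopsies on day 42" (± 4). Section 6.3 makes 6-week cycles discretionary. The Study Schema and Sections 1.3, 5.1, 8.0 and 9.3 give day 28 ± 4 of the cycle without this exception.

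**The concern.** A minimum is an extreme value. Its expected level depends on how many measurements it is drawn from as well as on the clearance it is meant to describe. Two patients with the same residual clone, one with 6 tracked variants and one with 25, get different depths.

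The larger problem is the correlation with time to progression. If the minimum runs across marrows and allele frequency is falling, each later marrow tends to lower it. A patient must remain on study and progression-free to give that marrow. Late progressors then show greater depth because they were observed longer, and the analysis cannot tell this from a real effect of clearance.

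Velocity and depth form the first-listed biomarker in the secondary objectives (Section 2.2), so a spurious link with progression could be reported as a main correlative finding. The power paragraph matters less, but a reader cannot tell which test the change-over-time figures support.

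**Working it through.** **1. Variant count and depth.** Inputs from Section 14.2.3: 6 to 25 variants, within-clone SD 3.2% (maximum observed 4.7%). For k normal values the expected minimum is the mean plus e(k) × SD, with e(6) = −1.267 and e(25) = −1.965.
- SD 3.2: 4.05 points below the clone mean for 6 variants and 6.29 for 25; gap 2.24.
- SD 4.7: 5.95 and 9.24; gap 3.29.
- With values floored at zero (SD 3.2), the gap is 2.2 points at a clone mean of 10% or more, 1.2 at 5%, 0.4 at 3% and 0.1 at 2%.

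**2. Number of marrows and time to progression.** The documents give no clearance half-life or progression time, so both are assumed, with a range. The fraction of allele frequency left at day t is 2^(−t/h).

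| Half-life h | Day 10 | Day 28 | Day 56 | Day 28 ÷ day 56 |
|---|---|---|---|---|
| 14 days | 0.61 | 0.25 | 0.06 | 4.0 |
| 28 days | 0.78 | 0.50 | 0.25 | 2.0 |
| 56 days | 0.88 | 0.71 | 0.50 | 1.4 |

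A patient who progresses between days 28 and 56 therefore has a depth value 1.4 to 4 times that of one who gives the cycle 2 marrow, with identical clearance. With exponential progression, the share progressing by day 56 is 1 − 2^(−56/120) = 28% at a median of 120 days and 1 − 2^(−56/240) = 15% at 240 days.

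A null simulation put these together: 100 patients, identical half-life, 6 to 25 variants, SD 3.2, starting clone mean 40% with between-patient SD 5, no marrow after progression, minimum across all marrows, rank correlation with time to progression at the 5% level, 300 runs per setting. The correlation was significant in every run at a median of 120 days, and in 94% to 100% of runs at 240 days, across the three half-lives. With the mean allele frequency at day 28, in patients progression-free then, the rate was 3% to 7%, consistent with 5% given simulation error.

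**3. Sampling day.** A patient in CRi at Cycle 1 Day 28 who starts 6-week cycles has the cycle 2 marrow at 28 + 42 = study day 70 (66 to 74 with the ± 4 window on that marrow). Section 14.2.3 labels it day 56. With half-lives of 14, 28 and 56 days, allele frequency at day 70 is 0.50, 0.71 and 0.84 of its day-56 value. A log rate divided by 56 instead of 70 would be inflated by 70/56 = 1.25; on actual days with constant clearance it would not change.

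**4. Change-over-time power.** Two-sided alpha 0.05 is assumed (sidedness is not stated). Unpaired test: noncentrality d/(SD × √(2/n)), df 2n − 2. Paired test: d√n/(SD × √(2(1 − ρ))), df n − 1, where ρ is the correlation between the two measurements of the same variant.

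| n, d, SD | Stated | Unpaired | Paired ρ = 0 | ρ = 0.5 | ρ = 0.6 |
|---|---|---|---|---|---|
| 6, 10, 3.2 | >99% | 99.8% | 98.8% | >99.9% | >99.9% |
| 3, 15, 3.2 | >98% | 98.6% | 81% | 96% | 98% |
| 6, 10, 4.7 | 91% | 91.2% | 83% | 98% | 99.5% |
| 3, 15, 4.7 | 82% | 82.8% | 55% | 79% | 85% |

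The unpaired test reproduces all four stated figures. The paired test does not do so at any one correlation: 91% in the third row needs ρ between 0 and 0.5, while 82% in the fourth needs ρ between 0.5 and 0.6.

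**The case against.** Much can be said for the plan, and several stronger readings that a reader might draw are not supported.

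- *Both biomarkers are artefacts of variant count.* No. Velocity is a log rate, not a minimum. Even for depth, variant count biases a comparison only if it differs between the groups compared, and nothing in the documents says that it does. Otherwise it adds noise.
- *Depth is certainly a minimum across marrows.* The wording refers to a single marrow sample and can be read either way. The immortal-time argument needs the across-marrow reading, and the text does not exclude it.
- *The bias is small.* With flat allele frequencies, 45 responders against 55 non-responders, and 20% to 40% of non-responders giving one marrow instead of three, the false-positive rate for depth against response is about 5% to 9% when the between-patient SD is 5 to 10 points (13% to 42% only with no between-patient spread). That is fair for flat allele frequencies. It does not carry over to time to progression when allele frequencies fall.
- *Responders are sampled later.* Only those with CRi or better early enough, on discretionary 6-week cycles, and only at the cycle 2 marrow. Both on-treatment cycle 1 marrows are scheduled alike for all.
- *Velocity is inflated by 25%.* Only if nominal days are used. No section requires that, and the Study Calendar Form records dates.
- *The ANOVA is specified to drop incomplete patients.* Section 14.2.3 has no such rule; it is silent on missing marrows.
- *The ±2.56% half-width is wrong.* It equals 1.96 × 3.2/√6, which is legitimate for an SD that the plan says it assumes.
- *The power is too low.* That depends on a correlation the plan does not state. At 0.6 the paired test meets all four figures.

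**Conclusion.** The point stands in limited form, as a change that should be made to a secondary, correlative analysis.

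Depth as defined depends on variant count (about 2.2 points between 6 and 25 variants at SD 3.2%, when allele frequency is well above zero). If taken across marrows, it also depends on time progression-free. Its correlation with time to progression then carries immortal-time bias. The size of that bias rests on assumed half-lives and progression times; its direction requires only that allele frequency falls and that marrows stop at progression. Velocity is exposed only through missing later samples or nominal days.

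The passages on the day of the cycle 2 marrow disagree for early CRi patients on 6-week cycles and must be reconciled. The change-over-time power figures do not match the named test. This is a mismatch of method and figure, not proof of inadequate power.

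**What to change.** - Define depth as the mean allele frequency of the validated variants at one fixed sample, for example Cycle 1 Day 28, with a detection-limit rule for zeros.
- Compute velocity on actual sample days, with the same rule for zeros before taking logs.
- Relate both to progression from a landmark at that sample, in patients progression-free then, and report how many are excluded.
- Analyse serial allele frequency with a linear mixed model on actual days. Keep the cycle 2 marrow in that model and as a supportive depth measure.
- Reconcile the cycle 2 sampling day across the Study Schema, Sections 1.3, 5.1, 5.2.9, 8.0, 9.3 and 14.2.3, and Appendix 2.
- Restate the change-over-time power for the paired test with its assumed correlation, or name the unpaired test that was used.

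The cost is SAP text and code; no new samples are needed. The downside is that the landmark excludes patients who progress before it, and clearance after the fixed sample is not in the main depth measure.

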6.1 Delay for Cytopenia or Infection

As cytopenias are a defining feature of AML and MDS, their presence alone does not generally warrant dose modifications or delays. Patients will receive four cycles of therapy without adjustment for any cytopenia. Following Cycle 4, dose modifications or delays for cytopenias will be made at the discretion of the investigator.

Patients with febrile neutropenia (temperature $\geq 38.5^\circ$ with ANC $< 1,000/\mu\text{l}$) or systemic infections should have treatment held until clinical resolution of the infection.

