14.2.4 Safety Analysis

Extent of Exposure – Duration (number of cycles/infusions) of decitabine doses (cumulative and intensity) will be summarized.

Adverse Events - All adverse events will be coded using NCI CTCAE v. 4.0. The incidence of treatment-emergent adverse events (number and percent of patients reporting the adverse event at least once during the study) will be summarized. In addition, adverse events will be summarized by investigator attribution of relationship to study medication and by grade. Similar summaries will be provided by treatment cycle.

Clinical Laboratory Evaluation – Applicable laboratory parameters will be graded according to NCI CTCAE version 4.0. The incidence of maximum grade (number and percent of patients experiencing the maximum grade during the study) will be summarized for each laboratory parameter. Similar summaries will be provided by treatment cycle. Graphical displays of select hematological parameters will also be provided.

Vital Signs, Physical Findings, and Other Safety Observations – Vital signs, findings from physical examinations, ECOG scores and weights will be presented in listing format.

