1.2.2 Experience with extended dosing schedules

Blum *et al* recently published their experience treating elderly AML patients with a 10-day course of decitabine 20 mg/m²/day as a 1-hour infusion.[3] This

prolonged exposure course was designed to increase the number of AML blast divisions exposed to decitabine per cycle. Toxicities were very similar to a similar regiment given as a 3 and 5 day course,[2, 16] but the overall response (CR/PR) was much improved (64% vs 25%). In all three studies, the toxicities were primarily myeloid suppression and the resultant infectious and bleeding complications associated with leukemic and pharmacologic hematopoietic suppression. Furthermore, Blum *et al* noted that the percent methylcytosine reduction was improved (22% vs 11%) as was the time to blast clearance (50% of patients who ultimately achieved a CR had $\leq 5\%$ bone marrow blasts after 1 cycle vs 0% of patients after 2 cycles). Finally, like Shen *et al*, they observed a correlation between the extent of methylcytosine reduction and response.[28] This study suggests that improvement in response rates and time to response can be achieved by prolonged administration of decitabine. Further, that DNA methylcytosine reduction can be achieved with prolonged exposure to decitabine and that this might be a patient-specific biological marker of adequate dosing.

Scandura *et al*. recently published a study of infusional decitabine prior to cytarabine + daunorubicin induction therapy for AML.[64] They escalated the duration of infusional therapy and reached their planned goal of 20 mg/m²/day x 7 days of continuous therapy given prior to cytarabine and daunorubicin. They noted similar toxicities (primarily hematopoietic and the associated neutropenic infections), but that these were not different from their experience giving cytarabine + daunorubicin alone.

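### The Day 10 methylcytosine comparison takes no account of how many decitabine doses preceded the marrow, so an association with non-response could not be attributed to poor drug effect rather than doses not given

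*Combined protocol and SAP*

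**What the plan says.** In the current protocol, Section 1.3 (item 5) fixes the measurement: "Patients will be evaluated pre-study and Cycle 1 Day 10" ± 1. Sections 5.2.6 and 8.0 schedule the marrow in the same window. Section 14.2.3 says "The percent decrease in bone marrow methylcytosine will be calculated on day 10" ± 1, and then "We will compare this reduction with previously published data and between the patients who achieve CR/CRi and those who do not". The test named for methylcytosine change is a repeated-measures two-way ANOVA with follow-up group comparisons. The power statement uses a two-sample t-test. Section 1.3 states what the result will show: "This will determine whether inadequate blast exposure to decitabine correlates with drug resistance".

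Dosing is planned for Days 1-10 but can be interrupted. Section 6.2 holds the next dose when renal or hepatic dysfunction arises during a course. Section 6.1 says that patients with febrile neutropenia or "systemic infections should have treatment held until clinical resolution of the infection". No section moves the Day 10 marrow after a hold, requires a minimum number of doses before it, or adjusts for doses given.

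Dose counts appear only under safety (14.2.4): "Duration (number of cycles/infusions) of decitabine doses (cumulative and intensity) will be summarized". Section 15.0 lists a Treatment Record Form kept through treatment. The one exposure variable in the methylcytosine analysis is the Day 4 ± 1 plasma level: "The change of total bone marrow DNA methylcytosine from baseline and its association with both steady-state plasma drug levels and response" are to be assessed together.

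**The concern.** The number of doses before the Day 10 marrow is not fixed by the calendar. A patient whose dosing stopped part-way through Cycle 1 may reach that marrow with far fewer doses than planned, and the analysis treats that patient like one who had the full course. The reasons for a hold, infection or organ dysfunction, are also plausible reasons for not reaching CR/CRi. Holds could therefore be commoner among non-responders and carry lower demethylation with them.

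What is at stake is attribution. An observed association would have two explanations: the drug was not given, or it was given and demethylated poorly. Only the second bears on resistance to the drug, and the planned comparison cannot separate them. The Day 4 plasma level is a single sample drawn during an infusion and cannot show how many doses had been given by Day 10. The efficacy-evaluable population (14.1) requires one cycle, sets no minimum dose count, and is not assigned to this analysis.

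**Working it through.** **Inputs from 14.2.3:** 45 responders, 55 non-responders, SD 15, design difference 20 (both read as percentage points), alpha 0.05 taken as two-sided. **Input from 1.2.2:** 22% reduction on the 10-day course against 11% in the comparison. This is readable only in an earlier protocol version in the same file, because the current Section 1.2 is redacted. **Assumed:** hold rates by response, and five doses missed by each held patient. The documents give neither.

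**1. The plan's own figure.** SE = 15 × √(1/45 + 1/55) = 3.02 points. The two-sided t-test has more than 99.99% power for 20 points, so the stated 99% holds as a floor. A gap reaches significance at about 1.96 × 3.02 = 5.9 points. The difference detectable with 80% power is (1.96 + 0.84) × 3.02 = 8.4 points.

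**2. Points per dose.** 22 − 11 = 11 points. Over 5 fewer doses (5-day comparator) this is 11/5 = 2.2 points per dose. Over 7 fewer (3-day comparator) it is 11/7 = 1.57. Both assume a straight line through a contrast between studies.

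**3. Gap from held doses alone.** Gap = slope × doses missed × (share of non-responders held − share of responders held). With five doses missed, 10% of responders held, and no true difference at equal dosing, 4,000 simulated trials per setting gave:

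| Non-responders held | Gap (points) | Unadjusted t-test rejects |
|---|---|---|
| 20% | 0.79-1.10 | 5.5-6.0% |
| 30% | 1.57-2.20 | 8.1-10.5% |
| 40% | 2.36-3.30 | 11.6-17.8% |
| 50% | 3.14-4.40 | 16.9-28.2% |

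Ranges run from slope 1.57 to 2.2. With dose count as a covariate, rejection was 4.6-5.6% throughout. In a more extreme case (seven doses missed, 10% against 50% held, slope 2.2), the gap is 2.2 × 7 × 0.4 = 6.2 points, and the unadjusted test rejected in about 45% of trials against about 5% adjusted.

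**4. Can holds produce 20 points?** The required difference in share held is 20/(slope × doses missed). At slope 2.2 this is 20/11 = 182% for five missed doses and 20/19.8 = 101% for nine. Neither is possible.

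**5. The ± 1 day window.** A Day 9 marrow before infusion follows 8 doses, and a Day 11 marrow follows 10. With equal shares at 8, 9 and 10 doses, the SD of dose count is √(2/3) = 0.82. The added SD is 0.82 × 2.2 = 1.8 points, and √(15² + 1.8²) = 15.1. The effect is negligible.

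**6. Cost of restricting to dosed patients.** At 10% against 50% held, about 40 and 28 patients remain (45 × 0.9 and 55 × 0.5). SE = 15 × √(1/40 + 1/28) = 3.70, and power for 20 points is still above 99.9%.

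**The case against.** A reader might infer that held doses will be mistaken for drug resistance. The documents do not support that. Section 1.3 uses demethylation as the marker of exposure and failure to respond as the resistance. The synopsis in earlier versions describes the assay as a possible marker of adequate dosing. A patient with held doses and low demethylation is then read as under-exposed, which is correct. What stands is narrower: the plan cannot say why exposure was low.

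A reader might also take the rejection rates above as false positives of the planned comparison. They are not. In those simulated trials non-responders really do have less demethylation, so rejection is right for the secondary objective in 2.2, which asks only about correlation. The rates are errors only for a claim about drug effect at equal dosing. For the same reason, replacing the planned comparison with a dose-adjusted one would change the question. Dose count is post-baseline and is part of exposure.

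The size is also open to challenge. Entry rules exclude active infection and limit organ dysfunction, and cytopenia alone triggers no adjustment for four cycles, so early holds may be uncommon. Section 6.1 does not expressly say that its rule acts mid-course; 6.2 does. The 22% against 11% contrast identifies neither comparator nor sampling day for the lower figure. These points limit the size and leave the gap in the analysis plan.

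**Conclusion.** The gap is real but modest. If holds are commoner in non-responders, an unadjusted association between low demethylation and non-response would mix three things: doses not given, the illness that caused the hold, and poor effect despite dosing. The size is unknown. It is negligible at 10% against 20% held and material only if holds differ widely between the groups. These figures rest on assumed hold rates, five missed doses and a linear cross-study slope. They cover missed doses only, not any direct effect of the illness. A 20-point difference could not plausibly be explained by holds. However, the plan sets no minimum difference for declaring an association, and gaps near 6 points would be significant. The endpoint is secondary, the primary mutation analysis is unaffected, and the Day 9-11 window needs no action.

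**What to change.** Keep the planned unadjusted comparison in 14.2.3 for the correlation objective. Pre-specify beside it:

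1. A linear model for methylcytosine reduction with response group and the number of decitabine doses given before the Day 10 marrow, taken from the Treatment Record Form. Confirm that the form dates each infusion.
2. A sensitivity analysis in patients with at least 8 doses by that marrow. This keeps every patient without a hold, wherever in the window the marrow fell.

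In 1.3, state that an association will be attributed to poor drug effect despite dosing only if it persists in both analyses. Otherwise it should be reported as under-exposure that includes missed doses.

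The cost is one degree of freedom, two extra analyses and a few sentences. Because dose count is post-baseline, the adjusted result supplements the unadjusted one and does not replace it. No change to the holding rules is implied.
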